#### 4.7. Dose Escalation Safety Monitoring Period

In Part A, the dose-escalation safety monitoring period is from the beginning of the IV administration of ANK-700 through the D15 clinic visit. Any AEs that meet the criteria defined in Section 4.6 but occur after the dose-escalation safety monitoring period of Part A, may be considered by the SMC in the evaluation for Part B dose selection.

The dose-escalation safety monitoring period in Part B is from the beginning of the first IV administration of ANK-700/PBO through the D22 clinic visit.

The monitoring period is supported by nonclinical animal data, which demonstrate:

- ANK-700 is cleared from circulation in < 7 minutes, ensuring that > 5 half-lives have elapsed during the safety monitoring period
- T-cell tolerance induction can be observed as early as 1 week after drug administration in nonclinical models, ensuring the mechanism of action will be active and robust during the safety monitoring period
- Immunologically active antigen cannot be detected in animals 7 days after GP-peptide administration, ensuring that any processed antigen will be cleared during the safety monitoring period

AEs and any abnormal clinical parameters, including laboratory findings, observed during this period will be used by the SMC to determine whether dose escalation should proceed.

No patient with a DLT will be replaced.

In both parts, patients will be monitored in the clinic for 8 hours after the completion the first IV administration of ANK-700/PBO. In Part B, patients will be monitored in the clinic for 4 hours after completion of their second and third dose.

## 4.8. SAFETY MONITORING COMMITTEE

This study will utilize an independent SMC that will meet regularly during dose escalation to review all accumulated and available data, including safety and PK. The SMC will be composed of 3 independent medical reviewers, including at least 1 medical expert in MS, as voting members. Non-voting members will include the study Medical Monitor, a medical representative from the Sponsor, and other relevant study and site staff as required to address study conduct. The SMC will make recommendations concerning dose escalation and/or any changes to the dosing paradigm based on review of the received data. The SMC will also make recommendations about the dose(s) selected for Part B. The final decisions related to dose escalation or the dosing paradigm will be made by the Sponsor.

#### 4.9. INDIVIDUAL AND COHORT STOPPING RULES

During the dose-escalation safety monitoring period, any DLT will result in a pause in enrollment and a thorough review by the SMC before treating any additional patients. Any ≥ Grade 4 AE will result in notification of the FDA in parallel with the SMC, and study dosing and enrollment will be paused pending review by FDA.

For Part A, if 1 of the first 3 patients experiences a DLT within the safety monitoring period (D1 to D15) in a given cohort, 3 additional patients will be enrolled and evaluated in that cohort before dose escalation can occur if recommended by the SMC and only after consultation with the FDA for any  $\geq$  Grade 4 AE. If 2 or more patients experience a DLT at a given dose level during the dose escalation evaluation period of Part A (D1 to D15), then that dose level will be considered to have exceeded the non-tolerated dose (NTD), and no further escalation will proceed.

If a patient experiences a DLT during the dose-escalation safety monitoring period of Part B, no additional doses will be administered to that patient. If 1 patient experiences a DLT during the dose-escalation safety monitoring period of Part B, the study will be paused to determine if any dose adjustments are needed and/or if the study should dose any additional patients. For any  $\geq$  Grade 4 AE, the study will only continue after consultation with the FDA. If 2 or more patients experience a DLT during the dose-escalation safety monitoring period of Part B (D1 to D22), then that dose level will be considered to have exceeded the NTD, and no further escalation will proceed.

The maximum tolerated dose (MTD) will be defined as the proximal dose level below the dose exceeding the NTD administered during the study. Of note, dose escalation may not identify an NTD or MTD.

#### 4.10. TREATMENT DISCONTINUATION

Patients will be discontinued from treatment for any of the after reasons:

- An AE that requires permanent discontinuation of study treatment\*
- Noncompliance with the protocol

Study ANK-700-01 in Relapsing-Remitting Multiple Sclerosis

- Investigator decision
- patient becomes pregnant
- patient death
- patient lost to follow-up
- termination of the study by the Sponsor
- voluntary withdrawal of consent by patient

The reason for treatment discontinuation will be documented.

All patients will have a final follow-up approximately 6 months (D182  $\pm$  7) after the single dose of ANK-700 in Part A and approximately 1 year (D365  $\pm$  14) after the first dose in Part B unless the patient withdraws from the study prematurely (Section 4.11).

#### 4.11. STUDY WITHDRAWAL

Patients may voluntarily withdraw from the study at any time for any reason without prejudice.

Patients will be withdrawn from the study for any of the following reasons:

- Investigator's decision
- Patient death
- Patient lost to follow-up
- Termination of the study by the Sponsor
- Voluntary withdrawal of consent by patient

\*AEs leading to the discontinuation of ANK-700 will be followed until resolution, resolution to baseline, or until the event is considered stable or chronic.

### 5. STUDY POPULATION

### 5.1. INCLUSION CRITERIA

ANK-700

- 1. Male or female adults aged 18 to 60 years inclusive at screening
- 2. Diagnosed with RRMS per revised McDonald criteria (2017) with an EDSS score ≤ 6.5 at screening
- 3. Neurologically stable with no evidence of relapse within the 28 days prior to signing the informed consent form (ICF)
  - Note: Patients who experienced relapse during the screening period (i.e., after signing the ICF but before dosing) may be rescreened after 28 days
- 4. Either not currently receiving disease modifying MS therapy or currently using fumarate drugs (i.e. dimethyl fumarate, diroximel fumarate)
  - Note: Patients on fumarate drugs are only eligible if they have been on a stable dose  $\geq 6$  months before administration of study drug
- 5. Patients must use a highly effective method of birth control or are sterile or postmenopausal as confirmed by study Investigator for the first 3 months (through D90) of the study
- 6. Patient has signed and understands the ICF

# **5.2.** EXCLUSION CRITERIA

- 1. Diagnosis of PPMS or SPMS
- 2. Uncontrolled or significant medical conditions (including active infection, chronic hepatitis, or Neuromyelitis Optica Spectrum Disorder) which, in the opinion of the Investigator, preclude participation
- 3. Has any of the following laboratory parameters at screening:
  - a. Hemoglobin < 10 g/dL
  - b. Platelet count  $< 100 \times 10^9/L$
  - c. White blood cell count outside the normal range and assessed as clinically significant by the Investigator
  - d. Alanine aminotransferase (ALT), aspartate aminotransferase (AST), or alkaline phosphatase (ALP)  $> 1.5 \times$  the upper limit of normal
  - e. Estimated glomerular filtration rate < 60 mL/min/1.73 m² based on the Cockcroft-Gault equation during screening
- 4. Positive for HIV, hepatitis B virus (HBV), or hepatitis C virus (HCV)
- 5. Patients treated with glatiramer acetate, parenteral steroids or adrenocorticotropic hormone,  $\beta$ -interferon, or plasma exchange within the 3 months prior to first dose
- 6. Patients treated with sphingosine-1-phospate receptor modulators such as fingolimod, ozanimod, or siponimod within 6 months prior to first dose

Anokion US, Inc.

7. Patients treated with cytotoxic agents (including but not limited to cladribine, mitoxantrone, cyclophosphamide, azathioprine, and methotrexate), laquinimod,

teriflunomide, or IV gamma globulin within 12 months prior to first dose

- 8. Patients treated with monoclonal antibody (mAb) therapy (including natalizumab, daclizumab, rituximab, and ocrelizumab) within 24 months prior to first dose except antisevere acute respiratory syndrome coronavirus 2 monoclonal antibodies
- 9. Patients receiving any vaccination within 28 days prior to first dose
- 10. Patients previously treated with alemtuzumab, total lymphoid irradiation, mesenchymal stem cell or hematopoietic stem cell transplantation, or tolerance-inducing therapies for MS
- 11. Patients with clinical signs and symptoms consistent with suspected COVID-19 or confirmed COVID-19 infection by appropriate laboratory test within the last 4 weeks prior to screening or on admission
  - Note: Patients who experienced symptoms consistent with COVID-19 or confirmed infection during the screening period (i.e., after signing the ICF but before dosing) may be rescreened after 4 weeks
- 12. Patients with a prior severe course of COVID-19 requiring extracorporeal membrane oxygenation or mechanical ventilation
- 13. Patient does not agree to limit alcohol intake to 2 drink equivalents or less per day during the study
- 14. Contraindication to or inability to undergo gadolinium-enhanced MRI scan
- 15. Use of any investigational drug or experimental procedure within previous 6 months that would interfere with the assessment of ANK-700
- 16. Patients who are pregnant or breastfeeding

Study ANK-700-01 in Relapsing-Remitting Multiple Sclerosis

### 6. STUDY PROCEDURES AND ASSESSMENTS

Time points for assessments collected throughout the study can be found in the Schedule of Assessments (Table 1 and Table 2). A brief description of each assessment can be found below.

### 6.1. SCREENING AND TREATMENT PROCEDURES AND ASSESSMENTS

### **6.1.1. Informed Consent**

An ICF must be signed by prospective patients before initiating any study-specific procedures. Standard of care assessments performed prior to ICF signing may fulfill study eligibility requirements if performed within the screening period. Patients will be required to sign ICF for rescreening.

### 6.1.2. Inclusion and Exclusion Criteria

Inclusion and exclusion criteria (Section 5) will be reviewed for each potential patient. Eligibility will be documented in the electronic case report form (eCRF).

# 6.1.3. Medical History, Demographics, and Disease History

Complete medical history will be obtained, including demographics, previous therapies, and disease history. MS is considered part of medical history and should include:

- duration since MS symptom onset
- duration since MS diagnosis
- number of relapses within the last year and 3 years
- date of last relapse
- previous MS treatment(s)

### 6.1.4. Concomitant Medications and Procedures

At screening, concomitant medications will be recorded. Assessment of any change in concomitant medications, or procedures since the last visit will occur at all further patient visits through the final Follow-Up Visit.

# 6.1.5. Expanded Disability Status Scale (EDSS) Assessment

Assessment of EDSS score will be captured at the time points specified in the Schedule of Assessments (Table 1 and Table 2). The EDSS is based on a standard neurological examination, incorporating the pyramidal, cerebellar, brainstem, sensory, bowel/bladder, visual, and cerebral [or mental] functional systems, and ambulation, rated and scored as functional system scores. The EDSS is a disability scale that ranges in 0.5-point steps from 0 (normal) to 10 (death) (Kurtzke 1983). The EDSS must be administered by a certified examiner. All patients with new

Study ANK-700-01 in Relapsing-Remitting Multiple Sclerosis

neurological symptoms suggestive of relapse may have an EDSS assessment performed during an unscheduled visit, if appropriate (see Section 11.1.2).

If the screening EDSS has been completed within 3 months of scheduled dosing it would not need to be repeated as long as the screen fail is not due to MS relapse. If the patient needs to rescreen due to experiencing an MS relapse during the screening period, the patient must wait at least 28 days from the relapse resolution and then a new screening EDSS should be obtained.

# 6.1.6. Physical Examination and Vital Signs

A full physical examination (PE) and vital signs check will be performed at the time points specified in the Schedule of Assessments (Table 1 and Table 2). PEs will also be conducted as clinically indicated.

The PE will include an assessment of general appearance, skin, head, neck, throat, lymph nodes, cardiovascular, neurological, thyroid, musculoskeletal/extremities, respiratory, abdomen, height, and weight (baseline only). Vital signs will include temperature, pulse rate, and diastolic and systolic blood pressure (sitting for 5 minutes). If vital signs need to be repeated during a single visit, assessments should be conducted approximately 5 minutes apart.

Any new clinically significant (CS) abnormality from baseline should be recorded as an AE.

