#### **Statistical Methods**

Statistical methods will be descriptive. No hypothesis will be formally tested. For Part A and Part B, summary statistics will be provided by cohort. For Part B only, placebo-treated patient data will be pooled. Categorical variables will be summarized using numbers and percentages. Continuous variables will be summarized by total number (n), mean, standard deviation, median, and range (minimum and maximum).

For the first dose, Part A and Part B will be pooled and summarized for demographic and PK analysis. A formal statistical analysis plan will be developed and finalized before study database lock.

Table 1: Schedule of Assessments Part A (SAD)

Assessment a	Screening	7		Stu	Early Term. b			
Study Day	-28 to 0	1 c	4±1	15	29±1	90±7	182±7	
Screening Assessments								
Informed consent	X							
Medical history/demographics	X							
Disease history	X							
Inclusion/exclusion	X							
ECG	X							
HIV, HBV, HCV testing	X							
Clinical Procedures								
Physical examination d	Xe							X
Pregnancy test	X f	X f,g			VC			
Vital signs h	X	Xg		X				X
Concomitant medications and procedures	X	X	X	X	X	X	X	X
EDSS i	X	Xg		X		X	X	
Safety Assessments								
Adverse events	X	X	X	X	X	X	X	X
Laboratory tests (safety)	X	Xg	X	X				X
MRI i	X j			Xk				
Study Drug Administration								
ANK-700 administration		X m						
Additional Blood Samples		•			7	•		
PK blood sample		$\mathbf{X}^{1}$	X					
ADA samples		Xg			X			X
						25		

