# Study ANK-700-01 in Relapsing-Remitting Multiple Sclerosis

a All patients should be contacted by site staff 1 day prior to each study visit for assessment of COVID-19 signs and symptoms.

- b Early termination visit only if patient discontinues within 28 days of dosing.
- c On D1 patients will be observed in the clinic/hospital unit for 8h after completion of IV infusion and followed up with by phone following discharge 24 hours after dosing.
- d Additional PEs will also be conducted as clinically indicated.
- e Includes weight at screening only.
- f Pregnancy test at screening must be serum; serum or urine tests are acceptable on Day 1 (D1) prior to dosing. Screening and D1 pregnancy test must be negative before ANK-700 is administered. Additional pregnancy monitoring per local guidelines may be implemented.
- g Samples/measurements to be taken pre-dose.
- h Vital signs include pulse rate, temperature, and diastolic and systolic blood pressure.
- i In the event of a suspected disease relapse, an unscheduled MRI and EDSS assessment may be performed if deemed clinically necessary.
- j The screening MRI must be performed ≥ 10 days prior to dosing on D1. For re-screening, the MRI only needs to be repeated if the previous assessment has been completed >3 months of scheduled dosing or if a relapse has occurred since last assessment.
- k The MRI at D15 may be performed up to 3 days before the D15 Visit.
- One PK sample will be taken pre-dose (≥at least 5 min prior to infusion), with all subsequent PK samples taken after the end-of-infusion (EOI) at the following time points: EOI 0 (+2) min, EOI 7 (±2) min, EOI 15 (±2) min, EOI 30 (±5) min, EOI 1 h (±5 min), EOI 2 h (±5 min), EOI 3 h (±5 min), EOI 4 h (±5 min), EOI 6 h (±5 min), and EOI 8 h (±5 min). PK samples to be taken from the arm that did not receive the infusion. The exact date and time of each sample collection must be recorded for all collected samples.
- m The prepared saline bag and infusion line should be weighed before and after administration. These weights should be recorded using any available scale with a precision to at least one tenth of a gram (0.1 grams). Both weight measurements should be conducted using the same scale to reduce variability.

Abbreviations: ADA = anti-drug antibodies; D=day; Early Term = early terminate	tion; ECG = electrocardiogram;
EDSS = Expanded Disability Status Scale;	t; h = hours; EOI =

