end of infusion; HBV = hepatitis B virus; HCV = hepatitis C virus;	; min =
minute; MRI = magnetic resonance imaging;	; PE = physical
examination; PK = pharmacokinetics; SAD = single ascending dose.	to disconditi

Table 2: Schedule of Assessments Part B (MAD) COHORT 4 ONLY

Assessments a	sments a Screening Treatment Period Study Period			10.57	Early Term. b					
Study Day	-28 to 0	1 c	4	7	22	43±2	90±7	182±7	365±14	
Screening Assessments	Screening Assessments									
Informed consent	X					9		3	4	
Medical history/demographics	X			3		51				,
Disease history	X							2, 3		
Inclusion/exclusion	X									
ECG	X					0.8 e	203 SI	203 20 207 70	. 15 . 15	e.
HIV, HBV, HCV testing	X									
Clinical Procedures		*				36. Y	34 3	59. 8	37.	
Physical examination d	Xe									X
Pregnancy test	Xf	$X^{f,g}$	$X^{f,g}$	$X^{f,g}$						
Vital signs h	X	Xg			X					
Concomitant medications and procedures	X	X	X	X	X	X	Х	X	X	X
EDSS i	X	Xg			X		X	X	X	
Safety Assessments									l.	M)
Adverse events		X	X	X	X	X	X	X	X	X
Laboratory tests (safety)	X	Xg	Xg	Xg	X					X
MRI i	$\mathbf{X}^{\mathbf{j}}$				$X^k$		$X^1$			
Study Drug Administration						30.	3.		•	
Randomization		X								
ANK-700 or PBO administration		X m,q	X n,q	X o,q						
Additional Blood Samples							•			
PK blood sample		Xº	Xg	$X^p$	X					
ADA samples		Xg			X		X	X	X	X
						US 8	203	203 80		
										5,0
76 <del></del>										

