# Study ANK-700-01 in Relapsing-Remitting Multiple Sclerosis

a All patients should be contacted by site staff 1 day before each study visit for assessment of COVID-19 signs and symptoms.

- b Early termination visit only if patient discontinues within 28 days of dosing.
- c On D1 patients will be observed in the clinic/hospital unit for 8h after completion of IV infusion and followed up with by phone following discharge 24 hours after dosing.
- d Pes will also be conducted on study as clinically indicated.
- e Includes weight at screening only.
- f Pregnancy test at screening must be serum; serum or urine tests are acceptable on D1, D4, and D7 prior to dosing. Screening and dosing day pregnancy tests must be negative before study drug is administered. Additional pregnancy monitoring per local guidelines may be implemented.
- g Samples/measurements taken pre-dose.
- h Vital signs include pulse rate, temperature, and diastolic and systolic blood pressure.
- i In the event of a suspected disease relapse, an unscheduled MRI and EDSS assessment may be performed if deemed clinically necessary.
- j The screening MRI must be performed ≥ 10 days prior to dosing on D1. For re-screening, the MRI only needs to be repeated if the previous assessment has been completed >3 months of scheduled dosing or if a relapse has occurred since last assessment
- k The MRI at D22 may be performed up to 3 days before the D22 visit.
-  The MRI at D90 may be performed within 2 weeks of the scheduled D90 visit.
- m On D1, patients will be observed in the clinic for 8 h after completion of IV infusion.
- n On D4 and D7, patients will be observed for 4 h after completion of IV infusion.
- o On D1, 1 PK sample will be taken pre-dose (≥ 5 min prior to infusion), with all subsequent PK samples taken after the end of infusion (EOI) at the following time points: EOI 0 (+2) min, EOI 7 (±2) min, EOI 15 (±2) min, EOI 30 (±5) min, EOI 1 h (±5 min), EOI 2 h (±5 min), EOI 3 h (±5 min), EOI 4 h (±5 min), EOI 6 h (±5 min) and EOI 8 h (±5 min). PK samples to be taken from the arm that did not receive the infusion. The exact date and time of each sample collection must be recorded for all collected samples.

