# 4.1. PART A – SINGLE ASCENDING DOSE

The SAD phase will include up to 3 cohorts with 3 patients each. Patients within each dose cohort will receive 1 dose of ANK-700 IV and will be monitored for up to 6 months. All patients in Part A will be dosed  $\geq$  14 days apart to monitor for acute and subacute reactions; this length of time is supported by nonclinical exposure data that suggest ANK-700 will have cleared > 5 half-lives and nonclinical animal model data demonstrating that the tolerance induction mechanism can develop and immunologically active peptide is cleared within 1 week from dosing (see Section 4.7 for more information).

Patients will arrive at the clinic on the morning of dosing (Day 1 [D1]) and will be monitored inclinic for 8 hours after completion of ANK-700 infusion for assessment of acute safety and PK blood sample collection. A follow up phone call 24 hours after dosing must be performed to ensure the patient did not experience any acute safety events after discharge.

- If patients are experiencing active AE(s) which require clinical monitoring at the end of the clinic/hospital unit monitoring period, they should not be discharged and followed up per PI assessment
- If feasible, patients should be advised to have someone stay with them after discharge until 24 hours have elapsed after study drug administration on D1.
- If patients do not live within 1-hour travel time of an emergency medical facility, they should remain in the clinic/hospital unit for the first 24 hours after study drug administration.
- Patients should be instructed not to drive themselves to seek emergency medical treatment at any time during the study.

Doses evaluated in Part A include 0.3 mg/kg (Cohort 1), 1.0 mg/kg (Cohort 2), and 3.0 mg/kg (Cohort 3). After all patients within a given dose cohort have been followed for ≥ 14 days post-dose, a safety review will be performed by the SMC to review all adverse events (AEs) and available clinical laboratory and PK data. Initiation of the next dose level will commence upon recommendation by the SMC and approval by the Sponsor.

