### 10.5. INFUSION-RELATED REACTIONS

If an IRR occurs during ANK-700 administration, the following treatment recommendations are provided and may be modified per local treatment standards and guidelines as appropriate.

- Grade 1 (mild): Infusion rate modification not indicated. Administer symptomatic treatment (e.g., antihistamines, antipyretics, antiemetics) as needed. Closely monitor patient until resolution. Prophylaxis with diphenhydramine 50 mg (or equivalent) and/or acetaminophen/paracetamol 325 to 1000 mg is recommended ≥ 30 minutes prior to future ANK-700 infusions.
- Grade 2 (moderate): Slow infusion to ≤ 50% of the original infusion rate and treat symptoms with appropriate medical therapy, including but not limited to antihistamines, antipyretics, and analgesics. Increase monitoring of vital signs as medically indicated until patient is deemed stable. Prophylaxis with diphenhydramine 50 mg (or equivalent) and/or acetaminophen/paracetamol 325 to 1000 mg is recommended ≥ 30 minutes prior to future ANK-700 infusions.
- Grade 3 (severe): Stop infusion and institute appropriate symptom-directed therapy, including but not limited to antihistamines, antipyretics, corticosteroids, bronchodilators, and oxygen. Increase monitoring of vital signs as medically indicated until patient is deemed stable. If the reaction has not resolved within 6 hours, the remainder of the infusion will not be administered, and ANK-700 will be permanently discontinued. After the completion or termination of a restarted infusion because of an IRR, all patients must be monitored until resolution of symptoms or for 2 hours in the absence of additional symptoms. Prophylaxis with diphenhydramine 50 mg (or equivalent) and/or acetaminophen/paracetamol 325 to 1000 mg is required ≥ 30 minutes before future ANK-700 infusions. The next infusion should initiate at a rate of 2 hours per dose, or 50% of the rate at which the reaction occurred. If no IRRs are observed within the first 30 minutes, the infusion rate may increase to the 1-hour-per-dose rate as outlined in Section 10.2. Permanently discontinue ANK-700 upon a second occurrence of a Grade 3 or greater infusion reaction.
- Grade 4 (life-threatening): Stop infusion and immediately institute appropriate symptom directed therapy and supportive measures as necessary, including, but not limited to, corticosteroids, bronchodilators, oxygen/respiratory support, and vasopressors.

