## 8.8.3 Vital Signs

Vital signs (temperature, pulse rate, and diastolic and systolic blood pressure will be summarized (as described in Section 7) for observed values and change from baseline, at each visit measured.

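### No routine vital sign is scheduled after any infusion before D15 (Part A) or D22 (Part B), so acute vital-sign changes cannot be summarised or compared with placebo

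*Protocol*

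**What the plan says.** The synopsis (Assessment of Safety) names vital signs as one of the safety measures. Protocol Section 6.1.6 leaves their timing to the schedule tables: a "vital signs check will be performed at the time points specified in the Schedule of Assessments". It allows repeats within a visit if needed but sets no time relative to an infusion.

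In Tables 1 to 3 the D1 entry carries footnote g, which reads "Samples/measurements to be taken pre-dose" for Part A and "Samples/measurements taken pre-dose" for Part B. The next scheduled reading is D15 in Part A or D22 in Part B. SAP Appendix 1 repeats this schedule.

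Section 4.1 keeps Part A patients in clinic "for 8 hours after completion of ANK-700 infusion for assessment of acute safety and PK blood sample collection". Section 4.2 gives the same purpose for the first infusion in Part B, and Section 4.7 adds a 4-hour stay after the second and third. For Grade 2 and Grade 3 infusion reactions, Section 10.5 instructs sites: "Increase monitoring of vital signs as medically indicated until patient is deemed stable". SAP 8.8.3 summarises vital signs "for observed values and change from baseline, at each visit measured".

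**The concern.** The plan holds patients in clinic to assess acute safety, and it names pulse, temperature and blood pressure among its safety measures. Yet it schedules none of these measurements during the stay. Section 10.5 speaks of increasing vital-sign monitoring when the schedule sets no routine level to increase from.

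Three things are at stake.

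- **The vital-sign results.** The only scheduled change from baseline after dosing is about two weeks or more after the last infusion. That analysis cannot show an acute effect, whether or not one occurred.
- **Adverse-event ascertainment.** Section 6.1.6 requires a new clinically significant abnormality to be recorded as an adverse event, and Grade 1 in Section 11.2.3 includes symptomless findings. A symptomless change in blood pressure, pulse or temperature can enter the primary endpoint only if someone measures it. With no set times, that may differ among the roughly 15 sites.
- **The placebo group.** SAP 3.1 says Part B was sized to allow a safety comparison with placebo. Readings prompted by a reaction have no fixed times and cannot serve as that comparison for vital signs.

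**Working it through.** No sample-size formula applies, because SAP 3.1 states that no such calculation was made. The check is a reading of the schedule followed by counting.

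**Step 1. Vital-sign rows, protocol Tables 1 to 3 and SAP Appendix 1.**

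| Part | Before dosing | After infusion, same day | Next scheduled reading |
|---|---|---|---|
| A, D1 | Yes | None | D15, or early termination if sooner |
| B, D1 | Yes | None | D22 |
| B, D4 | None | None | D22 |
| B, D7 | None | None | D22 |

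Both Part B cohorts have the same pattern. In Part A, D4 (a non-dosing visit) is also blank. The early-termination visit applies only to discontinuation within 28 days of dosing. Its column includes vital signs in Part A but not in Part B.

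**Step 2. Planned infusions.** The synopsis gives 9 to 18 patients in Part A (one infusion each) and 24 in Part B (16 ANK-700, 8 placebo; three infusions each).

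- Part A: 9 × 1 = 9 to 18 × 1 = 18.
- Part B: 24 × 3 = 72, of which 16 × 3 = 48 are active and 8 × 3 = 24 are placebo.
- Total: 9 + 72 = 81 to 18 + 72 = 90. Active: 9 + 48 = 57 to 18 + 48 = 66.

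**Step 3. Infusions with a scheduled same-day reading.**

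- After infusion: 0 of 81 to 0 of 90.
- Before infusion: D1 only, so 9 + 24 = 33 of 81 to 18 + 24 = 42 of 90. The other 24 × 2 = 48 infusions, on D4 and D7, have none.

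**Step 4. Time from infusion to the next routine reading.**

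- Part A: D15 − D1 = 14 days.
- Part B: D22 − D1 = 21 days; D22 − D4 = 18 days; D22 − D7 = 15 days.

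**Step 5. Contrast with drug sampling.** Tables 2 and 3 time 10 post-infusion PK draws on D1, from the end of infusion to 8 hours, and 8 on D7, to 4 hours. Table 1 has the same 10 on D1. No vital sign is paired with any of them.

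**Step 6. What the analysis can contain.** SAP Section 8 leaves vital signs out of the Part A summary tables, and protocol Section 12.5 says Part A safety data are listed. Scheduled data therefore give a Part B change from baseline at D22, and Part A readings at D15 or early termination. Neither describes the hours after an infusion.

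One inconsistency lies alongside. The clinic stay after the first infusion is 8 hours in Sections 4.1, 4.2 and 4.7 and in the schedule footnotes, but 24 hours in the synopsis (Assessment of Safety) and in SAP 2.3.2. These statements must be reconciled; the count of zero does not depend on which applies.

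**The case against.** The strongest reply is that the trial measures tolerability mainly through adverse events. The primary endpoint is the incidence and severity of TEAEs. Adverse events are collected on every dosing day, patients are observed after every infusion, a phone call follows 24 hours after the first dose, and infusions are supervised by medically qualified staff. Section 10.5 grades infusion reactions and adds vital-sign monitoring at Grades 2 and 3. All of this stands. A reader might infer that the trial cannot describe acute tolerability at all; the documents do not support that.

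A reader might also infer that the SMC would take a flat vital-sign table as reassurance when escalating. No section says the SMC receives the SAP 8.8.3 output. Sections 4.1 and 4.2 describe its reviews as adverse events with available laboratory and PK data, and Section 4.7 adds abnormal clinical parameters. False reassurance is conjecture. What can be said is that the only scheduled post-dose vital-sign input is late.

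Nor does the expected plasma half-life below 7 minutes (Section 4.2) prove that every effect is immediate. The drug acts through the immune system, and Section 4.7 relies on effects over about a week. The gap exists whatever the half-life.

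Finally, sites may take readings as routine infusion practice, or under a Pharmacy Manual that is not available here. The protocol and SAP neither require such readings to be recorded nor set their times, so they would not yield comparable data. It is also true that SAP 8.8.3 is consistent with the schedule and promises no acute comparison between groups. That makes this a weakness in what is collected rather than a contradiction in the analysis.

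**Conclusion.** The point holds in a limited form. None of the 81 to 90 planned infusions has a scheduled same-day post-infusion vital sign, and 48 Part B infusions have no same-day pre-dose reading either. Acute changes in pulse, blood pressure or temperature cannot be summarised or compared with placebo from scheduled data, and symptomless changes are the most likely to be missed. Acute tolerability rests on observed adverse events and infusion reactions, which remain informative.

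The counts assume planned enrolment with all infusions given and no replacements. The zero does not change with enrolment. The size of any missed effect is unknown, because the documents give no figure for it. The conclusion also assumes that no unseen manual fixes times for these readings and requires them to be recorded.

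**What to change.** In protocol Tables 1 to 3 and SAP Appendix 1, add recorded vital signs before dosing on D4 and D7 and at fixed post-infusion times within the existing 8-hour and 4-hour stays. The sponsor should choose times that allow the 5-minute seated rest in Section 6.1.6 and do not collide with the end-of-infusion PK draw, which has a +2-minute window and uses the arm not infused. D4 has only a pre-dose PK sample, so post-infusion readings that day need their own times.

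In SAP 8.8.3, summarise change from the same day's pre-dose value by time point and treatment group in Part B, with placebo pooled, and list it in Part A. Reconcile the new schedule with the wording on increased monitoring in Section 10.5.

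The cost is schedule and eCRF wording plus modest recording and data entry, with no new visit or staff. The pre-dose additions are 24 × 2 = 48 readings, and each fixed post-infusion time used on every dosing day adds 81 to 90. Enrolment was planned from autumn 2020 and the SAP is dated November 2022, so patients treated before the change would lack these readings. Each summary should state the number measured.

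If the schedule is not changed, state in the SAP that the 8.8.3 summary does not address acute effects.
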